2.3 Analyses of secondary outcomes

For our secondary outcomes a) episodes with self-reported infectious disease morbidity reported through the monthly follow-up calls, b) episodes with self-reported infectious disease morbidity suspected to be caused by COVID-19 (three or more of the following: fever, cough, sore throat, extreme fatigue, loss of smell and/or taste) and f) reported consultation for infectious disease, we will analyse repeated events data sets including all individuals for whom information was obtained through the telephone follow-up.

For the separated components of the composite outcome the population depends on the outcome assessed: c) mortality is for all individuals, d) hospital admissions for all individuals for whom a telephone follow-up was conducted and e) recorded consultation for all individuals alive in the study area.

The analyses of the secondary outcomes are described in more detail in table 2, 3 and 4.

¹If we identify evidence for non-proportionality, we will still report the marginal hazard ratios, but supplement this estimate by hazard ratios for 2-3 properly selected categorical time-periods identified based on the aforementioned proportionality investigations.

² If there is indication of non-proportionality based on assessment of the log-log curves, we will test for non-proportionality by replacing the term `tezp(_t)` with `tezp(_t>s)` for specific values of `s`.

Table 2: Analyses of secondary outcomes (a, b, d, f) – reported morbidity outcomes

Population	Per-protocol population
Observation period	From: enrolment To: 183 days after enrolment Censoring: Death, Date of loss to follow-up (last telephone interview)
Failure definition	
 a) Self-reported infectious disease morbidity. b) Self-reported infectious disease morbidity suspected to be caused by COVID-19 d) Hospital admission for infectious disease f) Reported consultation for infectious disease 
Repeated events. Episodes within 2 weeks of each other will be considered as related to the same infection. Thus, a trial participant will re-enter the population-at-risk 14 days after the episode start, provided that there has been a period without reported symptoms in the meantime.

Statistical tools	Repeated Cox-proportional hazards model, adjusted for the zone (stratification variable in the randomisation), age and box1 factors. Robust standard error to adjust for same-house clustering.
Outline stata code for analysis:	<pre>stset outdate2³, f(outcome=1) origin(dateenrol) time0(datestart) exit(censoring_date) id(study number) stcox group b11.zone b50.agegroup b1.box1var1 b1.box1var2 ..., vce(cl house)</pre> 
Where [box1var1] [box1var2] etc. are the background factors from Box1 which affect the [group]-estimate for the main outcome by more than 10%

Table 3: Analyses of secondary outcomes (c) - mortality

Population	Per-protocol population
Observation period	From: enrolment To: 183 days after enrolment Censoring: Migration
Failure definition	Death due to any cause
Statistical tools	Cox-proportional hazards model, adjusted for the zone (stratification variable in the randomisation), age and box1 factors. Robust standard error to adjust for same-house clustering.
Outline stata code for analysis:	<pre>stset outdate, f(death=1) origin(dateenrol) enter(dateenrol) exit(dateenrol+183) stcox group b11.zone b50.agegroup b1.box1var1 b1.box1var2 ..., vce(cl house)</pre> 
Where [box1var1] [box1var2] etc. are the background factors from Box1 which affect the [group]-estimate for the main outcome by at least 10%

³ Where outdate2 is the date of debut of symptoms and datestart is the date of enrolment or 14 days after a previous episode.

Table 4: Analyses of secondary outcomes (e): Recorded consultation due to infectious disease.

Population	Per-protocol population
Observation period	From: enrolment To: 183 days after enrolment Censoring: Death
Failure definition	Recorded consultation due to infectious disease. Repeated events. Episodes within 2 weeks of each other will be considered to be related to the same infection. Thus, a trial participant will re-enter the at-risk-population 14 days after the episode start, provided that there has been a period without reported symptoms in the meantime.
Statistical tools	Repeated Cox-proportional hazards model, adjusted for the zone (stratification variable in the randomisation), age and box1 factors. Robust standard error to adjust for same-house clustering.
Outline Stata code for analysis:	stset outdate2⁴, f(outcome=1) origin(dateenrol) time0(datestart) exit(censoring_date) id(study number) stcox group b11.zone b50.agegroup b1.box1var1 b1.box1var2 ..., vce(cl house) Where [box1var1] [box1var2] etc. are the background factors from Box1 which affect the [group]-estimate for the main outcome by more than 10%

⁴ Where outdate2 is the date of debut of symptoms and datestart is the date of enrolment or 14 days after a previous episode.

2.4 Additional analyses of primary outcome.

2.4.1. Effect-modifier analyses of primary outcome. Background factors known at enrolment.

We will assess whether the effect of the intervention on the primary effect measure is modified by the potential effect modifiers sex, presence of a BCG and/or smallpox vaccination scar, age, visual weight-score, and season of enrolment.

Table 5. Potential effect modifiers of the primary outcome – fixed during observation period

Population	Per-protocol population
Observation period	From: enrolment To: 183 days after enrolment Censoring: None
Potential effect modifiers	Sex Presence of a BCG vaccination scar Presence of a smallpox vaccination scar Age Visual weight-score Season of enrolment (Rainy: June-November, Dry: December-May)
Failure definition	Death or first post-enrolment admission for infection and/or consultation for infection.
Statistical tools	Cox-proportional hazards model with interaction term, adjusted for the zone (stratification variable in the randomisation), age and box1 factors. Robust standard error to adjust for same-house clustering.
Outline stata code for analysis:	<code>stset outdate, f(combinedoutcome=1) origin(dateenrol) enter(dateenrol) exit(dateenrol+183)</code> <code>stcox group#EfM EfM b11.zone b50.agegroup b1.box1var1 b1.box1var2 ..., vce(cl house)</code> Where EfM is the potential effect modifier (categorical variable) and [box1var1] [box1var2] etc. are the background factors from Box1 which affect the [group]-estimate for the main outcome by more than 10%

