1.4.1 Telephone follow-up

We called all study participants every 4 weeks between enrolment and 6 months of follow-up to collect information on health outcomes. In some cases, information was provided by a relative in the same household. For all trial participants, we asked whether they, since enrolment (for the 1st telephone interview call) or since the last call, had experienced any of the following symptoms:

Common cold, Cough, Fever, Breath-lessness, Vomiting, Diarrhoea, Loss of sense of smell, Loss of sense of taste, Headache, Sore throat, Body aches, Extreme tiredness, Other symptoms (If yes: which?)

For "yes" to either of these symptoms, further questions on timing were asked (today, within the last week, 1-<2 weeks ago, 2-<3 weeks ago, 3 or more weeks ago)

Information was also collected on:

Use of other medicine than habitual, COVID-test performed (and result thereof), Weight loss during the interval

Finally, all participants were asked if they had sought consultation or been admitted to hospital during the interval. If yes, they were asked when, where, reason for consultation/admission and whether they had received a diagnosis.

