1.6.3 Missing data

No outcome data will be imputed. However, for a particular event, we will assume that it was not caused by an infection if no information is obtained. Some dates of events may be imprecise (e.g., unknown date of consultation or only month of event known) – such dates will be allocated to the midpoint of the range of possible dates. As all individuals are followed for mortality through the HDSS, individuals whom we were not able to contact by telephone will still contribute to the assessment of the main outcome.

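### For symptom outcomes a and b, stretches with missed calls stay at risk although episodes older than three weeks cannot be dated or separated; unequal call completion could then bias the hazard ratio

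*SAP*

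**What the plan says.** SAP 1.4.1 sets the schedule: "We called all study participants every 4 weeks between enrolment and 6 months of follow-up". Each interview asks "whether they, since enrolment (for the 1st telephone interview call) or since the last call, had experienced any of the following symptoms". For a symptom that is reported, the timing classes are "today, within the last week, 1-<2 weeks ago, 2-<3 weeks ago, 3 or more weeks ago".

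SAP 2.3 analyses outcomes a, b and f in repeated-event data sets "including all individuals for whom information was obtained through the telephone follow-up", with no minimum number of interviews. In Table 2 observation runs from enrolment to day 183, with "Censoring: Death, Date of loss to follow-up (last telephone interview"). Footnote 3 fixes when risk time opens: "datestart is the date of enrolment or 14 days after a previous episode". Table 2 also requires a symptom-free period before a participant re-enters the risk set.

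On missing data, SAP 1.6.3 states "No outcome data will be imputed" and places imprecise dates at the midpoint of the possible range. It has no rule for a call that is missed and followed by one that is answered. Calls missed after the last interview are dealt with, because censoring removes that time.

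**The concern.** The questionnaire suits four-week intervals. In a regular interval the oldest timing class covers only days 21 to 28. Take a participant who answers calls 1 and 6 and misses calls 2 to 5. The last interview must cover 168 − 28 = 140 days. Only the latest 21 days are dated by week, and the other 119 days (17 weeks) share one class. Several illnesses may be recorded there as one, or not at all, and a symptom-free period between them cannot be shown. The midpoint rule would date such an episode (21 + 140)/2 = 80.5 days before the interview. SAP 2.5.1 extends the season and COVID-wave analyses to these outcomes, so the episode could land in the wrong period.

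Table 2 nevertheless counts all 140 days as observed on the same footing as five regular intervals. If one arm has more such gaps, its measured rate can fall without any vaccine effect. Outcome b is the only listed secondary outcome specific to COVID-19, and SAP 1.6.2 uses the secondary outcomes to judge whether the main finding is robust.

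**Working it through.** The plan gives no figure for these outcomes, so there is none to reproduce. The check asks what rate ratio the Table 2 rule yields when OPV has no effect.

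**Inputs from the SAP:** six calls 28 days apart (days 28 to 168); risk time from enrolment to the last interview; the timing classes in 1.4.1; midpoint dating in 1.6.3.

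**Assumed, because the documents are silent:** the probability *p* that a call is answered (80% v 70%, or 90% v 70%), independent between calls; 0.15 to 0.5 episodes per 28 days; and the share *r* of episodes older than 28 days that is remembered (100% or 50%). Ratios are better-reached over worse-reached arm.

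**1. Forgetting alone.** Let *c* be the share of counted time that lies within 28 days before an answered call. Enumerating all answered/missed patterns gives *c* = 0.917, 0.835 and 0.754 at *p* = 0.9, 0.8 and 0.7. Ignoring the 14-day re-entry gap, measured rate = true rate × [*c* + *r*(1 − *c*)].

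- *r* = 1: the bracket is 1 in both arms, so the ratio is 1.00.
- *r* = 0.5: the brackets are 0.917 + 0.5 × 0.083 = 0.959; 0.835 + 0.5 × 0.165 = 0.917; 0.754 + 0.5 × 0.246 = 0.877. The ratios are 0.917/0.877 = 1.05 (80% v 70%) and 0.959/0.877 = 1.09 (90% v 70%).
- *r* = 0, an outer bound outside the main range: 0.835/0.754 = 1.11 and 0.917/0.754 = 1.22.

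**2. Forgetting and merging.** Simulation under no effect, with at most one datable episode per interview:

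| Completion | Full recall | 50% recall beyond 28 days |
|---|---|---|
| 80% v 70% | 1.018–1.047 | 1.053–1.068 |
| 90% v 70% | 1.030–1.089 | 1.109–1.136 |

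Separate runs put the highest value at 1.13 to 1.14, a difference due to simulation error. With full recall and every episode recorded separately, the ratio is about 1.00.

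**3. Outcome b.** It needs three or more listed symptoms, so its rate is probably lower. At an assumed 0.02 to 0.05 episodes per 28 days and full recall, the ratio is 1.00–1.01 (80% v 70%) and 1.01–1.02 (90% v 70%). A larger bias for b has to come from forgetting.

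**4. Would a plain 28-day window be enough?** After one missed call the oldest class spans days 21 to 56, with midpoint 38.5. Such an episode is dropped, while days 21 to 28 stay in the denominator. In a regular interval the midpoint is 24.5 and the episode is kept. The share of answered calls that close a regular interval is *s* = (1 + 5*p*)/6, that is 0.917, 0.833 and 0.750 at 90%, 80% and 70%. The measured rate is proportional to *s* + (21/28)(1 − *s*) = 0.979, 0.958 and 0.938. The ratios are 0.958/0.938 = 1.02 and 0.979/0.938 = 1.04, so some bias remains.

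**5. A window that matches the classes.** Count the full interval when the previous scheduled call was answered, and only the last 21 days when it was missed. Each counted day is then one that the classes can date, and simulation returns about 1.00.

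**6. Episodes set aside at 80% completion.** Share kept = 0.835 × 0.958 / [*c* + *r*(1 − *c*)]. At *r* = 1 it is 0.80, so 20% are set aside. At *r* = 0.5 it is 0.80/0.917 = 0.87, so 13% are set aside. Merging lowers the loss further, to roughly 10%.

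**The case against.** A reader might infer that missed stretches are simply unobserved, and hence that the arm answering fewer calls must show fewer infections. The documents do not support this. The interview asks back to the last call, so a gap is asked about at the next contact, at least if last call means last completed interview, which the SAP leaves undefined. With full recall and separate recording there is no bias. Two conditions are needed: unequal completion by arm, and loss or merging of older episodes.

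A reader might also infer unequal completion from the high refusal rates in SAP 1.6.1. Those refusals occurred at enrolment, and nothing links them to answering calls among people who consented. The Protocol collects as many telephone numbers as possible, and SAP 1.4.1 lets relatives answer. If those who accepted OPV were the more willing to answer, the bias would run against OPV.

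One datable episode per interview is also an assumption. The follow-up questionnaire (Protocol Appendix 6) is not in the text reviewed, and different symptoms may carry different timings.

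These objections stand and limit the claim. They do not supply the missing rule: no passage says how intervals with missed calls are handled, and the open class cannot date or separate episodes across a long gap.

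**Conclusion.** The concern holds in conditional form. For outcomes a and b, Table 2 and footnote 3 treat long recall intervals as equal to regular ones, and the timing question cannot support that. With no true effect, the false rate ratio is about 1.00–1.07 for 80% v 70% completion and 1.00–1.13 for 90% v 70%. It depends on assumed completion, episode rates and recall. The documents do not show that completion differs, nor which arm would gain. For outcome b, symptoms from separate illnesses sharing the open class could also pass for one three-symptom episode, so even the direction is less certain there.

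The primary outcome does not use this rule. Outcomes d and f share Table 2, but participants were asked when an admission or consultation took place, so the open class does not apply to them. Because SAP 1.6.2 sets no significance threshold for secondary outcomes, the priority is modest.

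**What to change.** 1. In SAP 1.4.1, define the last call as the last completed interview.
2. Report, by arm, the number of completed calls and the length of the recall interval at each interview.
3. For outcomes a and b, add to Table 2 an analysis, at least as a prespecified sensitivity analysis, that limits risk time to what the timing classes support. Count the whole interval when the previous scheduled call or enrolment was about four weeks earlier, and only the last 21 days before the interview when a call was missed. Treat the earlier part as a gap through time0(), and leave out episodes placed in the oldest timing class in those intervals.

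The cost is one rule and one data step, since the outline code already uses time0(). Roughly 10–20% of reported episodes are set aside if 80% of calls were completed. If completion and recall length prove similar in the two arms, the planned analysis can stand with that table beside it.

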1.4.2 Passive case detection

All participants were informed that they could seek consultation free of charge at two health centres in the study area. Following a consultation at the health centre, information on date of consultation, symptoms, diagnostic tests, and prescribed treatment were collected from the health centres consultation books.

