1.5.2. Secondary outcomes

The secondary outcomes are other measures of infectious disease morbidity (prespecified: a and b, specified after trial initiation: f) and the three separate components of the composite outcome (c, d, and e).

a) Episodes with self-reported infectious disease morbidity: Through the telephone follow-up any reported episode which includes Common cold, Cough, Fever, Breath-lessness, Vomiting, Diarrhoea, Sore throat, or Body aches will be counted as an infectious disease episode. Following an infection, the person will re-enter the at-risk-population 2 weeks later.

b) Episodes with self-reported infectious disease morbidity suspected to be caused by COVID-19: Through the telephone follow-up any reported episode which includes three or more of the following: fever, cough, sore thought, extreme fatigue, or loss of smell/loss of taste). Following an infection, the person will re-enter the at-risk-population 2 weeks later.

c) Mortality: All-cause mortality: Death due to any cause during the follow-up period. If there are cases of inconsistency between different sources of information, the HDSS information will be considered superior.

d) Hospital admission: Hospital admission for infectious disease. Self-reported admission with symptoms or diagnosis classified as caused by infection. Analysed as a repeated event. Following an admission, the person will re-enter the at-risk-population 2 weeks later.

e) Consultations for infectious disease: Consultation for infectious disease registered at one of the two health centres. Analysed as a repeated event. Following a consultation, the person will re-enter the at-risk-population 2 weeks later.

f) Reported consultations: Any consultation for infectious disease reported to have occurred at any health facility.

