2.2 Primary analysis of primary outcome

The rates of the primary outcome (a composite outcome of the first of death, hospitalisation for infection and/or consultation for infection at the health centre) within 6 months after enrolment will be compared in Cox proportional hazards models with time since enrolment as the underlying timescale.

The primary analysis of the primary outcome is described in more detail in table 1.

Table 1: Primary analysis of primary outcome

Population	Per-protocol population
Observation period	From: enrolment To: 183 days after enrolment Censoring: None
Failure definition	Death or first post-enrolment admission for infection and/or consultation for infection registered at a health centre.
Statistical tools	Cox-proportional hazards model, adjusted for the zone (stratification variable in the randomisation) and age. Robust standard error to adjust for same-house clustering.
Outline stata code	<pre>stset outdate, f(combinedoutcome=1) origin(dateenrol) enter(dateenrol) exit(dateenrol+183) stcox group b11.zone b50.agegroup b1.box1var1 b1.box1var2 ..., vce(cl house) Where [box1var1] [box1var2] etc. are the background factors from Box1 which affect the [group]-estimate by at least 10% Check of proportional hazards assumption¹: estat phtest, detail stphplot, adj(zone agegroup box1var box2var) strata(group)² stcox group, strata(zone agegroup box1var box2var) vce(cl house) /// tvc(group) tezp(_t)</pre>

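### SAP Tables 2 and 4 time admissions and consultations by symptom onset, which the consultation books are not described as giving, and their re-entry rule conflicts with section 1.5.2

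*SAP*

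**What the plan says.** SAP Table 2 covers outcomes a, b, d and f, and Table 4 covers e. The code in both uses `outdate2` as the failure date, and footnotes 3 and 4 define it in the same words: "Where outdate2 is the date of debut of symptoms and datestart is the date of enrolment or 14 days after a previous episode".

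The data sources are described in section 1.4. For health-centre consultations (1.4.2), "information on date of consultation, symptoms, diagnostic tests, and prescribed treatment were collected from the health centres consultation books". For contacts reported by telephone (1.4.1): "If yes, they were asked when, where, reason for consultation/admission and whether they had received a diagnosis". The same call asks about individual symptoms, and for each one present "further questions on timing were asked (today, within the last week, 1-<2 weeks ago, 2-<3 weeks ago, 3 or more weeks ago".

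Section 1.5.2 defines re-entry for e as follows: "Following a consultation, the person will re-enter the at-risk-population 2 weeks later". It gives the matching rule for d, counted from the admission, and no rule for f. Tables 2 and 4 instead let a person re-enter 14 days after the episode began, on condition that a symptom-free interval has intervened.

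For the primary composite, Table 1 defines failure as "Death or first post-enrolment admission for infection and/or consultation for infection registered at a health centre". Its code uses a different variable, `outdate`, which is not defined in words. Section 1.6.3 states a midpoint rule for inexact dates: "Some dates of events may be imprecise (e.g., unknown date of consultation or only month of event known".

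**The concern.** Symptom onset is a natural event date for a and b, which are built from reported symptoms. Outcomes d, e and f are health-care contacts, and the recorded date is that of the contact. A footnote that times them by onset asks the analyst for a date that, for e, the described source does not supply.

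Three things follow. First, section 2.3 analyses e in everyone alive in the study area, and Table 4 censors only at death, so e does not depend on the telephone. If onset has to come from the telephone, it does. Second, two analysts following the same SAP can count different numbers of d and e events, because section 1.5.2 and the tables start the re-entry clock at different points. Third, section 1.6.2 uses the separate components to test whether the primary finding is robust. If d and e are dated by onset and the composite by contact, an illness that began before enrolment and led to a consultation afterwards is a primary event, yet in d or e its failure date precedes entry.

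**Working it through.** **Which date is asked for, and which is available**

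| Outcome | Date required by the footnote | Date the described source gives | Can the rule be applied? |
|---|---|---|---|
| a, b | symptom onset | symptom timing in weekly bands (call) | yes, approximately |
| d, f | symptom onset | when the admission or consultation took place (call) | only by borrowing a symptom band, with no rule for which symptom |
| e | symptom onset | consultation date (books) | no; the books are not described as giving onset |

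For e, onset would have to be imported from the call. That is a different source, it asks about symptoms one by one, and its last band is open-ended. A participant with a recorded consultation but no completed call has no onset date at all.

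**Re-entry rule, worked example for e.** Count days from the first onset. Suppose onset on day 0, consultation on day 7, recovery, new onset on day 16, and a second consultation on day 18.

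- Section 1.5.2: re-entry on day 7 + 14 = 21. The second consultation (day 18) falls before that, so there is one event.
- Table 4 with footnote 4: re-entry on day 0 + 14 = 14. The second onset (day 16) falls after that, so there are two events.

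The same participant contributes one or two events depending on which part of the SAP is followed. The symptom-free condition adds a further difference, since the books are not described as recording intervals without symptoms.

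**Share of contacts with onset before enrolment.** The documents give no onset-to-contact lag, so this is an assumption. With a constant contact rate over the 183-day window and a lag of L days, contacts in the first L days have onset before enrolment, so the share is L/183:

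- L = 3: 3/183 = 1.6%
- L = 7: 7/183 = 3.8%
- L = 14: 14/183 = 7.7%

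These are upper values, because people with acute current infection were not invited (SAP 1.1).

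**Effect on the hazard ratio.** The plan has no figure on this point to reproduce. As an illustration, the protocol's risks of 10% and 7.2% with constant hazards give HR = ln(1 − 0.072)/ln(1 − 0.10) = 0.709. A simulation of single events with exponential lags gave:

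| Mean lag, control / OPV (days) | HR by onset | HR by contact | HR if onset and contact must both fall in the window |
|---|---|---|---|
| 3 / 3 | 0.711 | 0.711 | 0.711 |
| 7 / 7 | 0.708 | 0.709 | 0.708 |
| 3 / 7 | 0.710 | 0.709 | 0.69 |
| 7 / 3 | 0.710 | 0.71 | 0.73 |

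Using either date consistently leaves the HR at about 0.71. It moves only when the lag differs by arm and both dates have to lie inside follow-up. The simulation uses the composite's planning risks and does not model repeated events, so it shows the order of magnitude only.

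**The case against.** The strongest reply is that this is a carried-over footnote. The two footnotes are identical and fit a and b. Section 1.5.2 defines e as a registered consultation and 1.4.2 supplies its date, so a sensible analyst would use that date. This is plausible, but the footnote is attached to Table 4, which covers only e, and the table's re-entry wording follows the same episode logic. The written rule still has to be corrected.

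Several stronger readings are tempting, and the documents do not support them:

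- **That the component analyses and the primary are shown to use two different dates.** `outdate` is never defined. The Table 1 failure definition and the example in 1.6.3 point to a contact date, but no sentence says so. The mismatch is an inference.
- **That it extends to f.** Section 1.5.2 names c, d and e as the components. f is not one and has no re-entry rule there, so neither the mismatch with the composite nor the conflict with 1.5.2 applies to it.
- **That nothing on onset is collected for d and f.** The same call that records the contact also records symptom timing in bands, and 1.6.3 allows midpoints. What is missing is a rule linking a symptom to a contact.
- **That 1.6% to 7.7% of events are lost.** The lags are assumed. Onset dating could also bring in contacts just after day 183 whose onset was earlier, a partial offset. How early records are handled depends on a dataset build that the SAP does not show.

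The objection also stands on consequence: the HR barely moves, and section 1.6.2 applies no significance threshold to secondary outcomes.

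**Conclusion.** The point holds as a defect in the rules for secondary outcomes d, e and f. It is clearest for e, where the written rule cannot be carried out from the described source and would leave consultations of people not reached by telephone without a failure date. For d and e the SAP also contradicts itself on when the re-entry clock starts, and the contradiction can change event counts. For d and f the gap is narrower: an approximate onset exists, but no linkage rule does. Different dating of d and e from the composite is likely on the wording but not established.

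The damage is to counts, completeness and reproducibility. A reader might infer bias in the trial's main result; the documents do not support that, because the primary analysis does not use `outdate2`. The HR shift for the secondary outcomes is expected to be small, provided one date is used consistently or lags are similar in the two arms. The share of contacts with onset before enrolment is at most about 1.6% to 7.7% for assumed lags of 3 to 14 days, and lower given the enrolment exclusion.

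**What to change.** In the SAP:

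1. Restrict symptom onset as `outdate2` to outcomes a and b.
2. For d, e and f, define `outdate2` as the date of the admission or consultation, with the midpoint rule of 1.6.3 where that date is inexact.
3. In Table 1, define `outdate` as the date of death, admission or consultation, so that d and e are visibly dated like the composite.
4. Start the 14-day re-entry for d and e from the contact date, as section 1.5.2 already says. State the same rule for f, where 1.5.2 is silent.
5. Drop the symptom-free condition for e. If it is kept for d or f, name the telephone item that establishes it.

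The cost is a few lines of SAP text and one date variable in the code. The contact dates are already collected under 1.4.1 and 1.4.2, so no new data are needed.
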